# GALDERMA

Doc id

#### 1.4 Safety Assessments

The methods for collecting safety data are described in Section 7 of the protocol. Data to be collected include the following:

- Adverse events.
- Subject diaries to be completed daily for 28 days following each treatment session. The presence and maximum intensity of pre-defined, expected post-treatment events, i.e., bruising, redness, pain, tenderness, lumps/bumps, itching and swelling shall be assessed for the treated area.
- Urine pregnancy test for women of childbearing potential performed at screening and all treatment visits (prior to treatment).
- Device deficiencies assessed at all treatment visits.

# 2 Statistical Methods

## 2.1 General Methods

Any change made to the finalized SAP before database lock will result in an SAP amendment. Otherwise, changes will be documented in the Clinical Study Report (CSR). However, if additional supportive or exploratory analyses are requested after SAP approval, this will not require amendment of the SAP, but these additional analyses will be described in the CSR.

Some of the analyses detailed here may be more explicit or in some respects different from those stated in the protocol. In case of differences, this SAP supersedes the statistical sections in the protocol.

# 2.1.1 Programming Conventions

**PPD** will have responsibility for performing analyses. All computations for statistical analyses will be performed using SAS® software, Version 9.4 or later. All SAS programs used in the production of statistical summary outputs will be validated prior to finalization as documented in the Quality Control Plan. In addition, all program outputs will be independently reviewed. The validation process will be used to confirm that all data manipulations and calculations were accurately done. Once validation is complete, a senior statistical reviewer will perform a final review of the documents to ensure the accuracy and consistency with this plan and consistency within tables. Upon completion of validation and quality review procedures, all documentation will be collected and filed by the project statistician or designee.

The electronic case report form (eCRF) data for all subjects will be included in the analysis datasets that are prepared for use in table and figure production.

# 2.1.2 Reporting Conventions

The formats for the tables, listings, and figures described in this SAP will be provided in a companion document. Changes to the formats of these reports that are decided after the finalization of the SAP will not require an amendment. In addition, any additional supportive or exploratory analyses requested after SAP approval will not require amendment of the SAP. These additional analyses will be described in the CSR.

**MA-58293** 

Doc id

Title	
05DF2209 Statistical Analysis Plan (SAP)	
GALDERMA	
GALDERMA	
EST, 1981	

Study data from the eCRFs as well as derived variables will be provided in subject data listings. An indication of specific listings for each data type will not be indicated in the text of subsequent SAP sections. Data listings supplied as part of the CSR will be sorted by study site number concatenated with subject number, treatment group, assessment dates, and/or time point.

The following conventions will be applied to all data presentations and analyses:

- Confidence intervals (CIs) will be two-tailed and constructed at a confidence level of 95%. Statistical tests will be performed at a significance level of 5%, and p-values will be two-sided, unless otherwise specified. CIs for responder rates will be calculated via Clopper-Pearson. CIs for the difference (Treatment No Treatment) in responder rates will be calculated via the normal approximation.
- Quantitative variables will generally be summarized by the number of subjects, mean, standard deviation, median, minimum, and maximum. Unless otherwise specified, the minimum and maximum values will be displayed to the same number of decimal places as the raw data, the mean and median will be presented to one extra decimal place compared to the raw data, and the standard deviation will be displayed to two extra decimal places compared to the raw data.
- Categorical variables will be summarized by the number and percentage of subjects (and number of events where appropriate) within each category. Unless otherwise specified, the percentage will be presented in parentheses to one decimal place. Frequency and percentage values of 0 will be presented as '0' rather than '0 (0)'.
- All summary tables will include the analysis population sample size (i.e., number of subjects) in each treatment group.
- Date variables will be formatted as DDMMMYYYY for presentation.

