#### 2.4.2 Handling of Missing Data

Number of missing values will be summarized and reported as appropriate.

For the ITT analysis of the Blinded Evaluator GJS Responder rate at Month 3 after last treatment for Treatment group (primary endpoint), missing values will be assumed to be

	Title	Doc id
	05DF2209 Statistical Analysis Plan (SAP)	
GALDERMA		MA-58293
EST, 1981		WIA-30293

missing due to lack of effect. Therefore, the primary method of imputation will use the baseline observation carried forward (BOCF) method. Impact of missing data on the primary endpoint will be evaluated by performing sensitivity analysis based on the observed cases, as well as worst-case (No Treatment group imputed as responder, Treatment group imputed as non-responder) and best-case (Treatment group imputed as responder, No Treatment group imputed as non-responder) imputation in the ITT set.

All other effectiveness endpoints will be evaluated based on the observed cases in ITT.

Descriptive statistics of all safety data will be performed on observed cases in the Safety population.

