# 2.4.3 Primary Effectiveness Analysis

Responder rate for each treatment based on the GJS, as assessed live by the Blinded Evaluator at 3 months after last treatment for the Treatment group and after baseline for the No Treatment group, will be the primary effectiveness endpoint. A responder will be defined as a subject with at least 1 grade improvement from baseline, on both jawlines concurrently.

The null hypothesis will be that there is no relationship between responder rate and treatment group (i.e., the responder rate is the same in treated and untreated subjects). The alternative hypothesis will be that there is a relationship between responder rate and treatment group (i.e., the responder rate is different in treated subjects compared to untreated subjects).

The estimates of the responder rate in each group will be presented as well as the difference in responder rates. Corresponding confidence intervals for responder rates (via Clopper-Pearson) and the difference in responder rates (via normal approximation) along with the p-value (via Fisher's exact test) for the difference will also be presented. For a significant result, the two-tailed p-value of the comparison of responder rates between the treated and untreated subjects at 3 months using the Fisher's exact test needs to be smaller than 0.05.

A forest plot of the treatment difference in Month 3 responder rates for the GJS will be provided.

[figure not shown]

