# 2.4.4 Secondary Effectiveness Analysis

(i) To assess the effectiveness of *Restylane Lyft Lidocaine* for Jawline definition, the following will be presented:

The responder rate on the GJS as assessed live by the Blinded Evaluator at 6, 9 and 12 months after last treatment for the Treatment group and after baseline for the No Treatment group will be presented as well as the difference in responder rates between groups. Corresponding confidence intervals for responder rates and the difference in responder rates will also be presented. A bar plot of the percentage of responders by visit will be produced for Blinded Evaluator and presented by treatment group.

The responder rates based on the GAIS as assessed by the investigator and the subject, respectively, at each visit will be calculated and presented along with their 95% confidence intervals for each treatment group. The difference in responder rate between the two groups will be presented along with a 95% confidence interval.

In addition, the GJS and GAIS (for subject and investigator) will be presented with number of subjects and percentage for each category of the scales for each visit by treatment group.

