#### 2.4.5 Subgroup Analyses

Supgroup analyses will be performed on age groups: less than or equal to median age, greater than median age. The statistical testing performed on the primary and secondary efficacy analyses will be repeated by age group.

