# 2.7 Determination of Sample Size

#### 2.7.1 Sample Size

A total sample size of approximately 140 subjects will be included in this study. For the responder rate in GJS, a Fisher's exact test using a 5% two-sided significance level will have approximately 90% power to demonstrate difference between a responder rate of 70% in the *Restylane Lyft Lidocaine* group, and a responder rate of 35% in the no treatment control group when the sample sizes are 105 and 35, respectively. Accounting for 10% dropouts, approximately 140 subjects need to be randomized in a 3:1 ratio.

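### The 95% CI for the difference in responder rates uses the normal approximation with about 35 controls; coverage falls modestly short, and a score interval corrects it at almost no cost

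*SAP*

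**What the plan says.** SAP 2.1.2 sets conventions for all presentations and analyses. On level and sidedness: "Confidence intervals (CIs) will be two-tailed and constructed at a confidence level of 95" per cent. For a single arm, "CIs for responder rates will be calculated via Clopper-Pearson". For the difference between arms, intervals "in responder rates will be calculated via the normal approximation".

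SAP 2.4.3 repeats this for the primary endpoint: "the difference in responder rates (via normal approximation) along with the p-value (via Fisher's exact test) for the difference will also be presented". The same section makes Fisher's two-tailed p below 0.05 the only condition for a significant result, and it adds a forest plot of the Month 3 difference.

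SAP 2.4.4 asks for intervals on the difference in GJS responder rates at 6, 9 and 12 months. For GAIS it says: "The difference in responder rate between the two groups will be presented along with a 95% confidence interval". These secondary endpoints use fewer subjects if data are missing, because under SAP 2.4.2 "All other effectiveness endpoints will be evaluated based on the observed cases in ITT". SAP 2.4.5 splits subjects at the median age and says: "The statistical testing performed on the primary and secondary efficacy analyses will be repeated by age group".

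The planning figures in SAP 2.7.1 are 70% against 35%, with 105 and 35 subjects. Protocol 9.4 asks for a 95% interval for the difference and names no method. Neither document explains the choice of the normal approximation or says whether a continuity correction is meant.

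**The concern.** The Wald interval takes its standard error from the observed proportions and is symmetric about the observed difference. With about 35 controls at a rate below one half, a control arm that happens to show few responders has two effects. It raises the estimated difference and it shrinks that arm's estimated variance. The interval is then narrowest when the estimate is too favourable, and its lower limit is too high more often than 2.5% of the time. Readers take that limit as the smallest plausible benefit, so the error favours the product.

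The limiting case is a control arm with no responders, which then adds nothing to the width. This could matter for GAIS, where untreated subjects are rated against their own baseline photograph. The documents give no GAIS rate, so how likely this is cannot be judged from them.

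What is at stake is the accuracy of the reported effect size and its forest plot. The test of the primary hypothesis is not at stake.

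**Working it through.** **Inputs.** From SAP 2.7.1: n1 = 105, n2 = 35, p1 = 0.70, p2 = 0.35, 10% dropout. The dropout figure gives 105 × 0.9 = 94.5 and 35 × 0.9 = 31.5, so 94/31 or 95/32 for observed-case endpoints. The primary analysis keeps 105/35, because missing values are imputed by BOCF. Assumed: an age half of 52/17, and every pair of rates other than 70/35. The normal approximation is read as unpooled and without continuity correction.

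**The plan's own figure.** The plan states about 90% power at 105/35. Exact Fisher power there is 95.0%; at 94/31 it is 92.0%. The literal sentence therefore does not reproduce. This is a separate, conservative wording matter and does not bear on the interval.

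**Formulas.** Write a = x1/n1 and b = x2/n2.

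- Wald: a − b ± 1.96 × √[a(1−a)/n1 + b(1−b)/n2].
- Miettinen-Nurminen (MN): all d with |a − b − d| ≤ 1.96 × √{[N/(N−1)] × [r1(1−r1)/n1 + r2(1−r2)/n2]}. Here N = n1 + n2, and r1, r2 are the maximum-likelihood rates under r1 − r2 = d.
- Coverage: the sum of Bin(x1; n1, p1) × Bin(x2; n2, p2) over all tables whose interval contains p1 − p2. A low miss means the lower limit lies above the true difference. A high miss means the upper limit lies below it.

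**Results by full enumeration** (coverage, with low/high misses in brackets):

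| Arms | True rates | Wald | MN |
|---|---|---|---|
| 105/35 | 70/35 (plan) | 94.1% (3.75/2.12) | 95.0% (2.39/2.62) |
| 94/31 | 70/35 | 93.9% | 95.0% |
| 95/32 | 70/35 | 94.2% | 95.1% |
| 52/17 (assumed) | 70/35 | 93.0% (4.8/2.3) | 95.0% |
| 105/35 | 80/20 (assumed) | 93.4% (5.0/1.6) | 95.2% |
| 105/35 | 90/10 (assumed) | 92.3% (6.8/0.9) | 95.0% (1.7/3.3) |
| 105/35 | 80/60 (assumed) | 93.8% (2.8/3.4) | 95.0% |

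The Newcombe interval at the plan covers 95.0%, with misses of 1.96% and 3.10%. The Wald lean towards a high lower limit holds for control rates below about 50% and disappears or reverses above that, as the last row shows. Mean width at the plan is 0.357 for Wald and 0.348 for MN, so precision is not lost.

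**A result near plan: 73/105 against 12/35.**

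- a = 0.6952, b = 0.3429, difference 0.3524.
- Variance = 0.2119/105 + 0.2253/35 = 0.00202 + 0.00644 = 0.00846; standard error 0.0920; half-width 0.1802.
- Wald: 17.2% to 53.3%. MN: 16.3% to 51.5%.

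**No control responders (assumed): 95/105 against 0/35.**

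- Difference 0.9048. Variance = 0.0862/105 + 0 = 0.00082; half-width 0.0561.
- Wald: 84.9% to 96.1%. MN: 80.1% to 94.8%.
- The Clopper-Pearson upper limit for the same control arm is 1 − 0.025^(1/35) = 10.0%. The report would therefore allow a control rate of up to 10% on one line and give it no uncertainty on the next.

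**Agreement with Fisher's test at 70/35, 105/35.** The interval excludes zero while p ≥ 0.05 in 1.04% of trials with Wald and 1.07% with MN.

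**The case against.** The strongest reply is that no conclusion changes. Fisher's test alone decides success, so type I error, power and sample size do not depend on this interval. At the only documented rates the shortfall is about 0.9 points, and in the near-plan example the lower limit moves by about one point. The method is standard, pre-specified and used consistently. All of this stands, and it is why the point ranks low.

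A second reply is that the SAP does not rule out a continuity correction. With one, coverage at the plan is 96.3% (misses 2.4% and 1.3%), so the interval would be conservative there. The uncorrected reading is the ordinary one, but the silence is real. Either reading misses 95%, and naming a score interval settles both.

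Third, the larger shortfalls come from assumed rates and an assumed subgroup split. That is correct. At a 35% control rate, zero responders among 35 has probability 0.65^35, about 3 in 10 million; at 10% it is 0.9^35 = 2.5%. The zero-responder case therefore matters only if an endpoint has a low control rate. The 70/35 rates are themselves planned for GJS at Month 3, so applying them to later visits is a further assumption.

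Fourth, SAP 2.4.5 speaks of repeating tests and does not mention intervals. The point reaches the age groups only if intervals are reported there, in which case the general convention in 2.1.2 governs them.

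**Conclusion.** The point holds, as a low-severity reporting refinement. At the planned sizes and rates the interval covers 94.1% instead of 95%, and the excess misses fall mainly at the lower limit (3.75% against 2.5%). The Miettinen-Nurminen interval restores 95.0% with nearly equal tails at those rates. At more extreme assumed rates its coverage stays near 95%, although its tails are no longer even (1.7%/3.3% at 90/10). The result assumes an unpooled interval without continuity correction. The primary decision is unaffected.

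**What to change.** In SAP 2.1.2 and 2.4.3, replace the normal approximation for the difference in responder rates with the Miettinen-Nurminen score interval. Apply it to the differences in 2.4.4 and to any reported under 2.4.5. Newcombe is an acceptable second choice, though its misses lean mildly towards the upper limit. Keep Fisher's exact test as the sole success rule, as now written, and keep Clopper-Pearson for single arms.

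Do not present the change as removing disagreement between interval and p-value: at the planning rates the frequency is about 1% with either method.

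The cost is a few words and one SAS option. If the SAP is already final and the database not yet locked, SAP 2.1 requires an amendment. A lighter route under SAP 2.1.2 is to add the score interval as a supportive analysis described in the CSR, but the Wald limits would then remain the primary ones. The downside is limits that differ slightly from the Wald limits, by about one point at the lower end near plan.

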# 2.2 Analysis Populations

The statistical analyses will be performed based on the following subject populations.

# 2.2.1 Safety Population

The Safety population includes all subjects who were treated with *Restylane Lyft Lidocaine* or were randomized to the No Treatment group at baseline. Subjects are analyzed according to the treatment actually received.

# 2.2.2 Intent-to-Treat (ITT) Population

The ITT population includes all subjects who were randomized. Subjects will be analyzed according to the treatment they were randomized to. All effectiveness variables will be analyzed based on the ITT population.

# 2.2.3 Per-Protocol (PP) Population

The PP population includes all ITT subjects who complete the visit 4 after baseline and are without any deviations considered to have substantial impact on the primary effectiveness outcome. The primary effectiveness analysis will be repeated using the PP analysis set if there is at least a 10% difference in the number of subjects between the PP and ITT sets.

Version: 1.0

# GALDERMA

Doc id

# 2.3 Study Subjects

Demographic endpoints, baseline assessments and subject characteristics will be summarized using descriptive statistics by treatment group and overall based on the ITT population using observed cases. There are no planned inferential statistical analyses of demographic endpoints or subject characteristics.

# 2.3.1 Subject Disposition

The number of subjects screened will be shown in total.

The number of subjects in each study population (i.e., ITT, PP, and Safety) will be summarized by treatment group and overall.

The disposition of subjects will be presented by treatment group, and in total, including numbers of subjects who were completed and withdrawn (including primary reason for withdrawal).

The number of subjects expected, completed, withdrawn, and missed will be summarized by scheduled visit, using the following definitions:

- Expected = all subjects at baseline minus subjects who have withdrawn up to that visit.
- Completed = subjects who showed up at that visit.
- Withdrawn = all subjects who have withdrawn up to that visit (cumulative).
- Missed = expected subjects minus completed subjects.

The end of study status will be listed for all subjects (both completed and withdrawn) individually, including at least subject number, end of study date, and last visit performed. In addition, reason for withdrawal will be provided for withdrawn subjects.

# 2.3.2 Protocol Deviations

Subjects with any protocol deviations will be summarized by treatment group, overall, and by type.

Depending on the seriousness of a protocol deviation, a subject might be excluded from the PP population, which shall be documented prior to database lock. Since the PP population includes subjects who complete the visit 4 or baseline, the focus will be on major deviations occurring before and at the Month 3 visit which are considered to have a substantial impact on the primary effectiveness outcome, see Table 3 below for list. Reasons for exclusion from the PP population also will be summarized.

# Table 3. Major Protocol Deviations Causing Exclusion from Per-Protocol Population

Major Deviation	
Month 3 visit out of window by greater than 21 days or earlier than 7 days	
Subject did not receive treatment as randomized	
GJS by Blinded Evaluator not done at Month 3 (primary endpoint)	
GJS by Blinded Evaluator not done at screening or baseline	

# Table 3. Major Protocol Deviations Causing Exclusion from Per-Protocol Population

#### **Major Deviation**

GJS by Blinded Evaluator at baseline is not grade 2 to 4 (moderate or very severe)

Prohibited concomitant treatments/procedures prior to Month 3 visit considered to have substantial impact on primary effectiveness outcome

Prohibited medical history, unstable medical history condition, or medical history condition that worsens prior to Month 3 visit considered to have substantial impact on primary effectiveness outcome

#### 2.3.3 Demographic Characteristics

Age and body mass index will be summarized as continuous variables.

Gender identity, sex at birth, race (including Asian subgroups), ethnicity, Fitzpatrick Skin Type (FST) score, childbearing potential, and baseline GJS (Blinded Evaluator) on the left and right side will be summarized as categorical variables.

## 2.3.4 Medical History, Medications, and Procedures

Prior and concomitant medications, vaccines, and procedural anesthetics will be coded using the World Health Organization Drug Dictionary (WHODD). Medical history, prior cosmetic treatments/procedures, and concomitant procedures/treatments will be coded according to the Medical Dictionary for Regulatory Activities (MedDRA).

Prior medications/procedures are the medications/procedures with stop dates prior to first study treatment session or randomization date for No Treatment group. Medications/procedures after the first study treatment session for Treatment group and after randomization date for No Treatment group will be considered concomitant.

Subjects reporting medical history, prior cosmetic treatments/procedures, and concomitant procedures/treatments will be summarized by System Organ Class (SOC) and Preferred Term (PT). Procedural anesthetics will only be listed.

Subjects reporting concomitant medications and vaccines will be summarized separately, by WHODD Anatomical Therapeutic Chemical (ATC) Class Level 3 (if Level 3 is not available, the highest class available will be used) and WHODD preferred name. Prior medications will only be listed.

# 2.4 Effectiveness Analysis

#### 2.4.1 Datasets Analyzed

The ITT population is primary for all effectiveness analyses. The primary effectiveness analysis will be repeated using the PP analysis population if there is at least a 10% difference in the number of subjects between the PP and ITT populations.

#### 2.4.2 Handling of Missing Data

Number of missing values will be summarized and reported as appropriate.

For the ITT analysis of the Blinded Evaluator GJS Responder rate at Month 3 after last treatment for Treatment group (primary endpoint), missing values will be assumed to be

	Title	Doc id
	05DF2209 Statistical Analysis Plan (SAP)	
GALDERMA		MA-58293
EST, 1981		WIA-30293

missing due to lack of effect. Therefore, the primary method of imputation will use the baseline observation carried forward (BOCF) method. Impact of missing data on the primary endpoint will be evaluated by performing sensitivity analysis based on the observed cases, as well as worst-case (No Treatment group imputed as responder, Treatment group imputed as non-responder) and best-case (Treatment group imputed as responder, No Treatment group imputed as non-responder) imputation in the ITT set.

All other effectiveness endpoints will be evaluated based on the observed cases in ITT.

Descriptive statistics of all safety data will be performed on observed cases in the Safety population.

